#### **4.9 Alternatives**

Measures will be taken to ensure the safety of patients participating in this study, including the use of stringent inclusion and exclusion criteria and close monitoring of patients during the study. Patients will be closely monitored for any adverse reactions or toxicities, and will be seen after each cycle to minimize risks. In addition, the patients will be undergo imaging to assess tumor progression. The alternative to participating in this study will the current standard of upfront surgical resection without neoadjuvant treatment. This will be offered to patients and presented as an option instead of enrolling in the clinical trial.

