#### **7.3.1 Adverse Event Reporting Period**

The study period during which all AEs and SAEs must be reported begins after informed consent is obtained and initiation of study treatment and ends 30 days following the last administration of study treatment or study discontinuation/termination, whichever is earlier. After this period, investigators should only report SAEs that are attributed to prior study treatment.

All adverse events (AEs), regardless of seriousness or relationship to study drug, are to be collected only on designated study dates from signing of informed consent through 30 days after administration of study drug, and recorded in the study-specific worksheets, with the following exceptions:

- AEs that are solely laboratory values; are not related to the study drug; AND are clinically non-significant may not be collected.
- Non serious AEs that are not related to the study drug; are not clinically significant; AND are expected in the post-surgery clinical setting may not be collected.
- SAEs that occur from signing of informed consent to prior to administration of study agent may not be collected unless assessed as possibly, probably or definitely-related to a study procedure.

All patients enrolled in this study receive surgical intervention in the course of their standard of care. As a consequence of this surgery, patients may experience certain

expected and normal adverse events. The following post-operative adverse events will be captured only in the patient's Electronic Health Record (EHR) source documentation and not in the adverse event log. If the adverse event exceeds the grading listed below or occurs outside the post-operative time window, the adverse event will be recorded in the Adverse Event Logs.

- Surgical wound site and associated, expected secondary signs and symptoms, including:
  - CTCAE v5.0 Grade 1 pain associated with surgical wound, including headaches – mild pain, little to no limit on adult daily life.
  - CTCAE v5.0 Grade 1 weight loss, anemia, and electrolyte abnormalities.

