## 9. STUDY CALENDAR

	Screening a	Treatment Cycles (21-day cycles)					Surgery	Follow-Up (or Treatment Discontinuation b )
		Cycle 1		Cycle 2		Cycle 3		
	Within 28 days prior to start of treatment	Day 1 (± 3 days)	Day 14 (± 7 days)	Day 21 (± 3 days)	Day 38 (± 4 days)	Day 42 (± 3 days)	2-4 weeks after Cycle 3	10 days ± 5 days after surgery (or < 30 days after last treatment)
Informed consent	X c							
Baseline tumor tissue sample d	X							
Second tumor tissue sample, if clinically feasible			X					
Demographic data	X							
Medical history and baseline conditions	X							
Vital signs e	X	X		X		X		X
Weight	X	X		X		X		X
Height	X							
Complete physical examination f	X							X
Limited physical examination g		X		X		X		
Digital Photography	X		X				X	
ECOG Performance Status	X							X
ECG h	X							
Hematology i	X j	X k		X		X		X

	Screening a	Treatment Cycles (21-day cycles)					Surgery	Follow-Up (or Treatment Discontinuation b )
		Cycle 1		Cycle 2		Cycle 3		
	Within 28 days prior to start of treatment	Day 1 (± 3 days)	Day 14 (± 7 days)	Day 21 (± 3 days)	Day 38 (± 4 days)	Day 42 (± 3 days)	2-4 weeks after Cycle 3	10 days ± 5 days after surgery (or < 30 days after last treatment)
Chemistry l	x j	x k		x		x		x
Pregnancy test m	x j							
Coagulation (INR, aPTT)	x j							
TSH n	x j							x
Urinalysis o	x j							
CT or MRI of primary site (if present) and regional lymphatics	x p				x p (prior to cycle 3)			
Chest CT with contrast or PET scan	x p							
Blood sample for exploratory biomarker research q	x		x				x	
Tumor response assessments s	x r	x s		x		x	x	
Concomitant medications t	x	x		x		x		x
Adverse events u	x u	x u		x u		x u		x u
Atezolizumab administration v		x		x		x		
Surgical resection							SOC	
Adjuvant Therapy w								SOC

	Screening a	Treatment Cycles (21-day cycles)					Surgery	Follow-Up (or Treatment Discontinuation b )
		Cycle 1		Cycle 2		Cycle 3		

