	Within 28 days prior to start of treatment	Day 1 ( $\pm$ 3 days)	Day 14 ( $\pm$ 7 days)	Day 21 ( $\pm$ 3 days)	Day 38 ( $\pm$ 4 days)	Day 42 ( $\pm$ 3 days)	2-4 weeks after Cycle 3	10 days $\pm$ 5 days after surgery (or < 30 days after last treatment)

ADA=anti-drug antibody; HBcAb=hepatitis B core antibody; HBsAb=hepatitis B surface antibody; HBsAg=hepatitis B surface antigen; NA=not applicable; PK=pharmacokinetic; T3=triiodothyronine; T4=thyroxine; TSH=thyroid-stimulating hormone; WES=whole exome sequencing; WGS=whole genome sequencing.

Notes: On treatment days, all assessments should be performed prior to dosing, unless otherwise specified.

Assessments shaded in gray should be performed as scheduled, but the associated data do not need to be recorded in the patient's medical records (except in the case of an adverse event).

- a Results of standard-of-care tests or examinations performed prior to obtaining informed consent and within 28 days prior to start of treatment may be used; such tests do not need to be repeated for screening.
- b Patients who discontinue study treatment will return to the clinic for a treatment discontinuation visit not more than 30 days after the last dose of study treatment. The visit at which response assessment shows progressive disease may be used as the treatment discontinuation visit.
- c Informed consent must be documented before any study-specific screening procedure is performed, and may be obtained more than 28 days before initiation of study treatment.
- d If archival tissue is unavailable or is determined to be unsuitable for required testing, a pretreatment tumor biopsy is required. A pretreatment tumor biopsy will also be performed, when clinically feasible, for biomarker assessment. Refer to Section 4.6 or tissue sample requirements.
- e Includes respiratory rate, pulse rate, and systolic and diastolic blood pressure, and temperature. Record abnormalities observed at baseline in the patient's medical records. At subsequent visits, record new or worsened clinically significant abnormalities in the patient's medical records. For the first and subsequent infusions, vital signs should be measured prior to the infusion (taken same day during clinic visit or in infusion area) and, if clinically indicated, during or after the infusion.

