## **12.3 Interim analyses**

Accrual will be limited to no more than 6 patients at a given window of immunotherapy dosing and 10 days post recovery from surgery. Toxicity and treatment failures will be reviewed prior to each additional patient accrual. If the number of patients who fail neoadjuvant treatment exceeds the maximum number allowable to achieve the primary objective, the study will be stopped early (i.e. treatment failure in 4 patients).

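### No adverse-event, medication or laboratory check is scheduled between dose 3 and surgery, which weakens attribution of dose-3 toxicity

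*Combined protocol and SAP*

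**What the plan says.** Section 7.3.1 states that adverse events "are to be collected only on designated study dates from signing of informed consent through 30 days after administration of study drug", and that the general reporting period "ends 30 days following the last administration of study treatment or study discontinuation/termination, whichever is earlier".

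The Section 9 calendar places dose 3 on Day 42, surgery "2-4 weeks after Cycle 3", and the next visit at "10 days ± 5 days after surgery (or < 30 days after last treatment". A general note to the calendar adds: "On treatment days, all assessments should be performed prior to dosing, unless otherwise specified".

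Other passages bear on the same question:

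- Section 4.9: "Patients will be closely monitored for any adverse reactions or toxicities, and will be seen after each cycle to minimize risks".
- Section 7.3.1 leaves certain post-operative findings in the health record only, among them "CTCAE v5.0 Grade 1 weight loss, anemia, and electrolyte abnormalities".
- Section 2.4 assesses adverse events until 30 days after the resection, not 30 days after the last dose.
- Calendar footnote u runs 30 days from the last dose for all events and 90 days for serious events and events of special interest, each ending sooner if new systemic anti-cancer therapy starts.
- Section 12.3: "Toxicity and treatment failures will be reviewed prior to each additional patient accrual".

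**The concern.** Doses 1 and 2 are each followed by a scheduled safety check before anything else is done to the patient: the assessment that precedes the next infusion. Dose 3 has no such check. The next scheduled event is an operation, and the next scheduled safety assessment comes after it.

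By then there is a second plausible cause for many findings. One limb of the causality guidance in Section 7.4 asks whether the event is readily explained by the clinical state or by other treatment, and after major surgery that explanation is at hand. Sections 4.7.1 and 4.7.2 also permit high-dose steroids on the day of surgery and afterwards, and Appendix I treats immune-related toxicity with corticosteroids, so a laboratory abnormality could change before it is first measured.

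Safety and tolerability is a secondary objective (Section 1.2), and Section 10.1 makes acceptable toxicity part of what feasibility means. The data are also meant to support the design of a larger trial of the same three-dose schedule.

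**Working it through.** The plan states no figure on this point, so there is none to reproduce. The check is a reading of the calendar followed by day arithmetic.

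**1. Calendar rows after the start of treatment**

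| Row | Day 1 | Day 21 | Day 42 | Surgery | Follow-up |
|---|---|---|---|---|---|
| Adverse events | yes | yes | yes | blank | yes |
| Concomitant medications | yes | yes | yes | blank | yes |
| Vital signs | yes | yes | yes | blank | yes |
| Hematology, chemistry | yes | yes | yes | blank | yes |
| TSH | blank | blank | blank | blank | yes |

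Apart from the resection, the Surgery column holds only photography, the biomarker blood sample and tumor response. Day 42 assessments are made before the infusion, so they cannot show an effect of dose 3. The first designated date that can is the follow-up visit. For TSH, the follow-up value is the only one scheduled after screening.

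**2. Gap after doses 1 and 2**

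- Dose 1 to next check: 21 − 1 = 20 days. With ±3 days at each end: 14 to 26.
- Dose 2 to next check: 42 − 21 = 21 days. With ±3 days at each end: 15 to 27.

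**3. Gap after dose 3**

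Gap = (dose 3 to surgery) + (surgery to follow-up). Inputs: 14 to 28 days, and 10 ± 5 = 5 to 15 days.

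- Surgery counted from dose 3: 14 + 5 = 19 to 28 + 15 = 43 days. At the nominal 10-day follow-up: 24 to 38.
- Surgery counted from the end of the 21-day cycle: 19 + 21 = 40 to 43 + 21 = 64 days.

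The calendar does not say which starting point is meant.

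**4. Gap against the 30-day window**

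Counting from dose 3:

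| Surgery on day | Follow-up on day | Permitted follow-up days past day 30 |
|---|---|---|
| 14 | 19 to 29 | 0 of 11 |
| 21 | 26 to 36 | 6 of 11 |
| 28 | 33 to 43 | 11 of 11 |

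There are 15 permitted surgery days and 11 permitted follow-up days, so 15 × 11 = 165 combinations. In 88 of them (53%) the follow-up visit comes after day 30. Counted from the end of the cycle, all 165 do. These are counts of permitted combinations, not forecasts.

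If the window is read by date of collection, a patient with such a late visit has no designated date between dose 3 and its closure. If it is read by date of onset, an event that began by day 30 can still be entered at the later visit. Section 7.3.1 does not say which applies.

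**The case against.** The strongest reply is that collection does not depend only on calendar marks. Section 7.3 makes the investigator responsible for every event observed or reported. Section 7.4 covers events volunteered or found by any means and records start date, end date and suspected relationship. Section 7.5.1 asks about events at every evaluation, which arguably includes the surgery contact. Footnote u follows serious events and events of special interest to 90 days, and Section 11.2 has the principal investigator tabulating events continuously. This stands for symptomatic and serious events. It does not create a designated pre-operative check or laboratory draw, and it conflicts with the restriction in Section 7.3.1 to designated dates.

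Several stronger readings are tempting and are not supported:

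- *Dose-3 toxicity cannot be told apart from surgical effects.* A symptom that began before the operation can be dated as such. Attribution is weakened, not lost.
- *Section 7.3.1 lets drug effects go uncollected.* Its exemption for expected post-surgical events applies only to those that are non-serious, unrelated to the drug and not clinically significant. The Grade 1 list covers post-operative findings only, and events outside the post-operative window go in the log, although that window is not defined.
- *Drug-related events will be under-counted.* Section 7.4 joins its criteria with and/or, so a surgical abnormality could equally be ascribed to the drug.
- *The Section 7.2 hold and Section 12.3 review run without dose-3 data.* Neither is tied to calendar visits, and an event reported between dose 3 and surgery would reach both. What they lack is scheduled dose-3 data for patients awaiting surgery.
- *Section 4.9 is flatly contradicted.* It promises that patients are seen, not that an adverse-event or laboratory assessment is made. The calendar simply has no safety entry that gives effect to it after cycle 3 and before surgery.

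Length alone is not the problem either. At its shortest, 19 days, the gap lies within the 14 to 27 days allowed after the earlier doses. What differs is that an operation falls inside it.

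**Conclusion.** The point holds in a limited form. No adverse-event, medication or laboratory assessment is scheduled between dose 3 and surgery, and the first designated safety date after dose 3 is post-operative: 19 to 43 days after the dose if surgery is counted from dose 3, 40 to 64 days if counted from the end of the cycle. That date can fall after the 30-day window has closed.

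The effect is weaker attribution of dose-3 toxicity, mainly for non-serious and laboratory-only events such as liver, renal, blood-count and thyroid changes. The direction of any bias is not established.

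It concerns patients who receive dose 3 and go on to surgery. Those who stop treatment have a visit within 30 days of the last dose. Those who decline surgery, whom Section 10.1 counts as having successfully received treatment, have no operation to confound the finding. The number affected therefore need not equal the 17 or more successes required in Section 12.1.

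This is a cheap improvement to a secondary objective. It is not a threat to the primary analysis.

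**What to change.** 1. In Section 9, mark Adverse events and Concomitant medications in the Surgery column as pre-operative, at the contact already used for photography, biomarker blood and tumor response. State in Section 7.3.1 that this is a designated study date.
2. Where hematology and chemistry are done before the operation as routine care, transcribe the results to the case report form. That such tests are done is an assumption: the documents schedule none after dose 3.
3. State whether the interval to surgery runs from dose 3 or from the end of cycle 3.
4. Reconcile the adverse-event windows (30 days after the last dose in Section 7.3.1 and footnote u, 30 days after resection in Section 2.4) and the collection rules (Section 7.3.1 against 4.9, 7.4 and 7.5.1).

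Counted from dose 3, the first designated adverse-event date would then fall at 14 to 28 days, before surgery and inside the 30-day window. Counted from the end of the cycle it would fall at 14 + 21 = 35 to 28 + 21 = 49 days, still before surgery but outside a window that runs from the last dose. Items 3 and 4 therefore belong with item 1.

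The cost is a few calendar marks, some clarifying text and a few more low-grade events in the log. No visit, dose or treatment rule changes.

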#### **7.4 Assessment of Adverse Events**

All AEs and SAEs whether volunteered by the patient, discovered by study personnel during questioning, or detected through physical examination, laboratory test, or other means will be reported appropriately. Each reported AE or SAE will be described by its duration (i.e., start and end dates), regulatory seriousness criteria if applicable, suspected relationship to atezolizumab (see following guidance), and actions taken.

To ensure consistency of AE and SAE causality assessments, investigators should apply the following general guideline:

##### **Yes**

There is a plausible temporal relationship between the onset of the AE and administration of atezolizumab, and the AE cannot be readily explained by the subject's clinical state, intercurrent illness, or concomitant therapies; and/or the AE follows a known pattern of response to atezolizumab or with similar treatments; and/or the AE abates or resolves upon discontinuation of atezolizumab or dose reduction and, if applicable, reappears upon re-challenge.

##### **No**

Evidence exists that the AE has an etiology other than atezolizumab (e.g., preexisting medical condition, underlying disease, intercurrent illness, or concomitant medication); and/or the AE has no plausible temporal relationship to atezolizumab administration (e.g., cancer diagnosed 2 days after first dose of atezolizumab).

Expected adverse events are those adverse events that are listed or characterized in the Package Insert (P.I) or current Investigator Brochure (I.B).

Unexpected adverse events are those not listed in the P.I. or current I.B or not identified. This includes adverse events for which the specificity or severity is not consistent with the description in the P.I. or I.B. For example, under this definition, hepatic necrosis would be unexpected if the P.I. or I.B. only referred to elevated hepatic enzymes or hepatitis.

## 7.5 Procedures for Eliciting, Recording, and Reporting Adverse Events

### 7.5.1 Eliciting Adverse Event Information

A consistent methodology of non-directive questioning should be adopted for eliciting adverse event information at all patient evaluation timepoints. Examples of non-directive questions include the following:

"How have you felt since your last clinic visit?"

"Have you had any new or changed health problems since you were last here?"

### 7.5.2 Specific instructions for Recording Adverse Events

Investigators should use correct medical terminology/concepts when reporting AEs or SAEs. Avoid colloquialisms and abbreviations.

#### 7.5.2.1 Diagnosis versus Signs and Symptoms

If known at the time of reporting, a diagnosis should be reported rather than individual signs and symptoms (e.g., record only liver failure or hepatitis rather than jaundice, asterixis, and elevated transaminases). However, if a constellation of signs and/or symptoms cannot be medically characterized as a single diagnosis or syndrome at the time of reporting, it is acceptable to report the information that is currently available. If a diagnosis is subsequently established, it should be reported as follow-up information.

#### 7.5.2.2 Deaths

All deaths that occur during the protocol-specified AE reporting period (see Section 7.3.1), regardless of attribution, will be reported to the appropriate parties. When recording a death, the event or condition that caused or contributed to the fatal outcome should be reported as the single medical concept. If the cause of death is unknown and cannot be ascertained at the time of reporting, report "Unexplained Death".

#### 7.5.2.3 Preexisting Medical Conditions

A preexisting medical condition is one that is present at the start of the study. Such conditions should be reported as medical and surgical history. A preexisting medical condition should be re-assessed throughout the trial and reported as an AE or SAE only if the frequency, severity, or character of the condition worsens during the study. When reporting such events, it is important to convey the concept that the preexisting condition has changed by including applicable descriptors (e.g., "more frequent headaches").

#### 7.4.2.4 Hospitalizations for Medical or Surgical Procedures

Any AE that results in hospitalization or prolonged hospitalization should be documented and reported as an SAE. If a subject is hospitalized to undergo a medical or surgical procedure as a result of an AE, the event responsible for the procedure, not the procedure itself, should be reported as the SAE. For example, if a subject is hospitalized to undergo coronary bypass surgery, record the heart condition that necessitated the bypass as the SAE.

Hospitalizations for the following reasons do not require reporting:

- Hospitalization or prolonged hospitalization for diagnostic or elective surgical

procedures for preexisting conditions

- Hospitalization or prolonged hospitalization required to allow efficacy measurement for the study or
- Hospitalization or prolonged hospitalization for scheduled therapy of the target disease of the study

#### 7.5.2.5 Assessment of Severity of Adverse Events

The adverse event severity grading scale for the NCI CTCAE (v5.0) will be used for assessing adverse event severity. Table 3 should be used for assessing severity for adverse events that are not specifically listed in the NCI CTCAE.

**Table 2 Adverse Event Severity Grading Scale for Events Not Specifically Listed in NCI CTCAE**

Grade	Severity
1	Mild; asymptomatic or mild symptoms; clinical or diagnostic observations only; or intervention not indicated
2	Moderate; minimal, local, or non-invasive intervention indicated; or limiting age-appropriate instrumental activities of daily living a
3	Severe or medically significant, but not immediately life-threatening; hospitalization or prolongation of hospitalization indicated; disabling; or limiting self-care activities of daily living b,c
4	Life-threatening consequences or urgent intervention indicated d
5	Death related to adverse event d

NCI CTCAE = National Cancer Institute Common Terminology Criteria for Adverse Events.

Note: Based on the most recent version of NCI CTCAE (v5.0), which can be found at: [http://ctep.cancer.gov/protocolDevelopment/electronic\\_applications/ctc.htm](http://ctep.cancer.gov/protocolDevelopment/electronic_applications/ctc.htm)

a Instrumental activities of daily living refer to preparing meals, shopping for groceries or clothes, using the telephone, managing money, etc.

b Examples of self-care activities of daily living include bathing, dressing and undressing, feeding oneself, using the toilet, and taking medications, as performed by patients who are not bedridden.

c If an event is assessed as a "significant medical event," it must be reported as a serious adverse event

d Grade 4 and 5 events must be reported as serious adverse events

#### 7.5.2.6 Pregnancies

If a female subject becomes pregnant while receiving atezolizumab or within 5 months after the last dose of atezolizumab, a report should be completed and expeditiously submitted to Genentech, Inc. Follow-up to obtain the outcome of the pregnancy should also occur.

Abortion, whether accidental, therapeutic, or spontaneous, should always be classified as serious, and expeditiously reported to Genentech as an SAE. Similarly, any congenital anomaly/birth defect in a child born to a female subject exposed to the atezolizumab should be reported to Genentech, Inc. as an SAE.

